9.6 Dietary or Other Protocol Restrictions

There are no dietary or other protocol restrictions for this study.

9.7 Safety and Efficacy Variables

As this is a first-in-man study, the primary endpoint of safety will be assessed as explained in Section 9.7.8.

The primary efficacy measure will be to assess plasma FVIII activity. The efficacy goal of the study is to establish the dose relationship to FVIII activity ≥ 5 IU/dL at 16 weeks post BMN 270 administration.

Proprietary and Confidential

9.7.1 Safety and Efficacy Measurements Assessed

The Schedule of Events (Table 9.1.1) describes the timing of required evaluations.

9.7.2 Primary Efficacy Variables

The primary efficacy measure will be the plasma FVIII activity monitored on a regular basis after BMN 270 dose. The efficacy goal of the protocol is to ascertain the dose range of BMN 270 required to convert severe HA patients to stable expression of FVIII at 5 IU/dL or above, i.e., a mild severity. This is associated in natural history studies with clinically superior long term outcomes, (Den Ujil, 2011, Haemophilia).

The following assays will be used to measure the primary efficacy variable:

- FVIII activity (chromogenic FXa assay)
- FVIII activity by one-stage APTT (Activated Partial Thromboplastin Time)

If a subject has used FVIII within 72 hours of a measurement day, all efforts should be made to obtain FVIII activity measurements when a 72-hour interval without FVIII use is achieved.

The FVIII activity level in both assays and the number of subjects with FVIII activity ≥ 5 IU/dL in at least one of the two assays will be summarized.

Timing of assessment by these assays is provided in Table 9.1.2 and Table 9.1.3. Details on performing the assays are included in the Laboratory Manual.

9.7.3 Secondary Efficacy Variables

Secondary efficacy measures will be the reduction in the frequency of factor replacement therapy, and reduction in the number of bleeding episodes. Subjects will be asked at each study visit to report the use of factor replacement therapy and the number of bleeding episodes since the previous visit. This information will be captured on the subject's diary or other subject records.

9.7.4 Immunogenicity

Immunogenicity assays will be performed on plasma. The assays will include detection of anti-capsid, and anti-FVIII total antibody, and determination of neutralizing antibodies against FVIII. Any increase in total antibody level, especially during the time period of 5-12 weeks, will be compared with FVIII activity measurements. Any abnormality of the liver parameters will lead to a retrospective immunogenicity assessment to determine anti-FVIII and capsid specific CTL. Anti-FVIII and capsid specific CTL assays will be performed on collected PBMCs.

Timing of assessment by these assays is provided in Table 9.1.2 and Table 9.1.3.

9.7.5 Pharmacodynamics

The hFVIII antigen and activity level will be measured by an ELISA (antigen) and by one-stage APTT and/or chromogenic FXa assay (activity). Individual antigen and activity plasma plots will be prepared to assess changes over 16 weeks. FVIII activity measurements will be used to determine PD parameters.

If supported by FVIII activity data, non-compartmental analysis and observation will be used to estimate individual values of C_b (baseline concentration), C_{ss} (steady state concentration), T_{ss} (time to steady state), C(t) and AUC(0-t) where t is 16 weeks. Other parameters that may be used to describe individual FVIII protein and activity plasma profiles are C_{max} (maximum concentration) and C_{avg} (average concentration, AUC(0-t)/t). The PD parameters and dose will be used to assess clinical pharmacology.

Sample collection times are indicated in Table 9.1.2 and Table 9.1.3.

9.7.6 Exploratory Biomarker Assessments

Blood samples will be collected from subjects at the time points indicated in Table 9.1.1 and Table 9.1.2 to evaluate biochemical, molecular, cellular, and genetic/genomic aspects relevant to Haemophilia A disease. The genetic/genomic testing on these exploratory samples is optional.

All biomarker samples collected in this study may be used for exploratory biomarker research including evaluation of additional biomarkers not specifically listed in the protocol. In addition, samples collected for other purposes may be used for exploratory use once the primary use has been completed. No additional genetic or genomic testing will be conducted on any sample (other than testing specified in the protocol).

9.7.7 Haemo-QoL-A Quality of Life Assessment

The Haemo-QoL-A is a patient-reported outcome (PRO) questionnaire which will be used to assess subject quality of life (QoL) during the study. Assessments will occur at the time points listed in the Schedules of Assessments.

Details regarding the QoL assessment will be included in the Study Reference Manual.

9.7.8 Safety Variables

Safety in this study will be determined from evaluation of AEs, clinical laboratory assessments with a particular attention to the liver function, vital signs assessments, physical examinations, and immunogenicity.

Proprietary and Confidential

9.7.8.1 Adverse Events

The occurrence of AEs will be assessed continuously from the time the subject signs the ICF. The determination, evaluation and reporting of AEs will be performed as outlined in Section 10. Assessments of AEs will occur at the time points shown in Table 9.1.1.

9.7.8.2 Clinical Laboratory Assessments

Specific visits for obtaining clinical laboratory assessment samples are provided in Table 9.1.1. The scheduled clinical laboratory tests are listed in Table 9.7.8.2.1. Refer to the Study Reference Manual for instructions on obtaining and shipping samples.

Any abnormal test results determined to be clinically significant by the Investigator should be repeated (at the Investigator's discretion) until the cause of the abnormality is determined, the value returns to baseline or to within normal limits, or the Investigator determines that the abnormal value is no longer clinically significant.

All abnormal clinical laboratory results should be initialed and dated by an Investigator, along with a comment regarding whether or not the result is clinically significant. Each clinically significant laboratory result should be recorded as an adverse event.

The diagnosis, if known, associated with abnormalities in clinical laboratory tests that are considered clinically significant by the Investigator will be recorded on the AE CRF.

Table 9.7.8.2.1:	Clinical Laboratory Tests
------------------	----------------------------------

Blood Chemistry	Haematology	Urine Tests	Other
Albumin	Haemoglobin	Appearance	CRP
Alkaline phosphatase	Haematocrit	Color	
ALT (SGPT)	WBC count	рН	Coagulation Screen including:
AST (SGOT)	RBC count	Specific gravity	APTT
Direct bilirubin	Platelet count	Ketones	PT/INR
Total bilirubin	Differential cell count	Protein	ТТ
BUN		Glucose	
Calcium		Bilirubin	
Chloride		Nitrite	
Total cholesterol		Urobilinogen	
CO ₂		Haemoglobin	
Creatinine			
Glucose			
GGT			
LDH			
Phosphorus			
Potassium			
Total protein			
Sodium			
Uric acid			

ALT, alanine aminotransferase; AST, aspartate aminotransferase; BUN, blood urea nitrogen; CO₂, carbon dioxide; GGT, gamma-glutamyltransferase; LDH, lactate dehydrogenase; PT, prothrombin time; APTT, activated partial thromboplastin time; RBC, red blood cell; SGOT, serum glutamic-oxaloacetic transaminase; SGPT, serum glutamic-pyruvic transaminase; WBC, white blood cell; TT, thrombin time; INR, international normalized ratio.

9.7.8.3 Liver function and Hepatitis Testing at Screening

Subjects will be screened for evidence of previous hepatitis B or hepatitis C infection at Screening. Subjects with documented results showing an absence of active Hepatitis B or Hepatitis C infection (as measured by positive surface antigen for hepatitis B or positive RNA testing for hepatitis C) 30 days prior to providing signed informed consent do not need to be screened again.

Evidence of ongoing Hepatitis B or Hepatitis C infection is exclusionary. Subjects who have cleared a Hepatitis B infection or are seronegative do not need to receive the Hepatitis B vaccination.

A liver ultrasound and liver function testing at Screening will identify any significant hepatic dysfunction, which is defined as:

- More than 3x the normal ALT level
- More than 3x the normal bilirubin level
- More than 3x the normal Alkaline phosphatase level.
- INR \geq 1.4.
- Thrombocytopoenia under $100 \ge 10^9/L$
- Liver ultrasound results indicative of a liver cirrhosis

9.7.8.4 Vital Signs, Physical Examinations and Other Observations Related to Safety

Vital signs will include seated systolic and diastolic blood pressure, heart rate, respiration rate, and temperature. Any clinically significant change in vital signs will be recorded as an AE.

Systolic blood pressure, diastolic blood pressure, heart rate, respiration rate, and temperature will be assessed at Screening, Baseline, and at the beginning of each visit during the Post-Infusion Follow-Up and Safety Follow-Up periods. On the day of the BMN 270 Infusion, vital signs will be monitored prior to infusion, during the infusion every 15 minutes (\pm 5 minutes), following the infusion hourly (\pm 5 minutes) for 6 hours and then every 2 hours (\pm 15 minutes) for 6 hours and then at 4 hour intervals (\pm 15 minutes).

A complete physical examination is necessary during Screening/Baseline; thereafter, brief physical examinations may be performed at the discretion of the investigator based on the subject's clinical condition. Particular attention should be given to signs of bleeding, as well as assessing possible hemarthroses.

A complete physical examination will include general appearance (head, eyes, ears, nose, and throat), cardiovascular, dermatologic, lymphatic, respiratory, gastrointestinal, genitourinary, musculoskeletal, and neurologic systems.

A brief physical examination will include general appearance, cardiovascular, respiratory, neurologic, and gastrointestinal assessments.

Weight and height will be recorded at Screening only.

9.7.8.5 Viral Shedding

Viral shedding has been extensively studied in all similar clinical trials performed to date. (Nathwani, 2014, N.Engl.J.Med.); (Manno, 2006, Nat.Med.); (Schenk-Braat, 2007, J.Gene Med.); (Croteau, 2004, Ann.Occup.Hyg.). In the literature referenced above, vector was no longer detectable after 40 days in blood, saliva, urine or stool. However, vector persisted in semen for 16 weeks in the seminal fluid but not in motile sperm (Manno, 2006, Nat.Med.). In all cases, the amount of vector present in these bodily fluids involved an extremely small fraction of the infused dose.

Viral shedding will also be extensively studied in the present clinical trial, every week up to 16 weeks, then every 4 weeks to one year, then every three months, until at least 3 consecutive negative results are obtained. During the Post-Infusion Follow-Up period, subjects will undergo testing of various bodily samples to look for evidence of viral shedding for possible viral transmission. Bodily fluids will be tested by PCR at the time points indicated in Table 9.1.2 and Table 9.1.3. Fluids tested will include:

- Blood
- Saliva
- Semen
- Urine
- Stool

Details for sample collection and storage are provided in the Laboratory Manual.

10 REPORTING ADVERSE EVENTS

10.1 Safety Parameters and Definitions

Safety assessments will consist of monitoring and recording protocol-defined AEs and SAEs; measurement of protocol-specified haematology, clinical chemistry, and urinalysis variables; measurement of protocol-specified vital signs; and other protocol-defined events of special interest that are deemed critical to the safety evaluation of the study drug.

10.1.1 Adverse Events

For this protocol, a reportable adverse event (AE) is any untoward medical occurrence (e.g., sign, symptom, illness, disease or injury) in a subject administered the study-drug or other protocol-imposed intervention, regardless of attribution. This includes the following:

- AEs not previously observed in the subject that emerge during the course of the study.
- Pre-existing medical conditions judged by the Investigator to have worsened in severity or frequency or changed in character during the study.
- Complications that occur as a result of non-drug protocol-imposed interventions (eg, AEs related to screening procedures).

An adverse drug reaction is any AE for which there is a reasonable possibility that the study-drug caused the AE. "Reasonable possibility" means there is evidence to suggest a causal relationship between the study-drug and the AE.

Bleeding events that are normal events of haemophilia (ie, bleeding events which occur only because the subject is a haemophiliac) should not be recorded as AEs but will instead be captured in subject diaries. Bleeding events that occur where a normal (ie, non-haemophiliac) patient would bleed, such as bleeding as a result of major trauma, should be recorded as adverse events. All bleeding events which meet criteria for being serious should be reported as serious adverse events (SAEs) whether or not they are bleeding events that are normal sequelae of haemophilia.

Whenever possible, it is preferable to record a diagnosis as the AE term rather than a series of terms relating to a diagnosis.

10.2 Serious Adverse Events

A serious adverse event (SAE) is any untoward medical occurrence that at any dose meets 1 or more of the following criteria:

- Is fatal
- Is life threatening

Note: Life-threatening refers to an event that places the subject at immediate risk of death. This definition does not include a reaction that, had it occurred in a more severe form, might have caused death.

- Requires or prolongs inpatient hospitalization.
- Results in persistent or significant disability or incapacity
- Is a congenital anomaly or birth defect in the child or fetus of a subject exposed to IP prior to conception or during pregnancy
- Is an important medical event or reaction that, based on medical judgment, may jeopardize the subject or require intervention to prevent one of the above consequences (e.g. anaphylaxis)

All adverse events that do not meet any of the criteria for SAEs should be regarded as nonserious AEs.

10.2.1 Events of Special Interest (EOSI)

The following EOSI need to be reported to the Sponsor within 24 hours of site awareness, irrespective of seriousness, severity or causality:

• Elevation of liver enzymes (ALT) that triggers a corticosteroid treatment

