9.3.3.1 Study Safety Evaluation Criteria

If any of the following events occur in a subject in the study who has received BMN 270 infusion, enrollment into the trial will be put on halt to complete an extensive safety analysis per Section 9.1.

- A 5-fold increase from baseline in ALT after BMN 270 administration
- The occurrence of Grade 3 or higher adverse events assessed as related to study drug, including liver failure and clinical hepatitis
- Grade 2 adverse event assessed as related to study drug that persists for at least 7 days
- The detection of neutralizing antibodies to hFVIII following BMN 270 infusion
- The persistent detection of the AAV vector genome in the semen of a participant more than 26 weeks after BMN 270 infusion, as discussed in Section 9.7.8.5
- The occurrence of a malignancy excluding skin cancers at any point after BMN 270 infusion

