10.5 Reporting Requirements

10.5.1 Expedited Reporting Requirements

All SAEs and EOSI that occur during the course of the AE Reporting Period (refer to Section 10.3.1), whether or not considered related to study drug, must be reported by entering the information in the AE eCRF and submitting to BPV within 24 hours of the site becoming aware of the event. Investigators should not wait to collect information that fully documents the event before notifying BPV of an SAE. BioMarin may be required to report certain SAEs to regulatory authorities within 7 calendar days of being notified about the event; therefore, it is important that Investigators submit any information requested by BioMarin as soon as it becomes available.

The Sponsor is responsible for identifying, preparing and reporting all SUSARs to the relevant competent authorities, ethics committees and investigators in accordance with the requirements identified in the Clinical Trials Regulations.

If the EDC is unavailable, all SAEs should be reported to BPV by completing the SAE Report Form and faxing or emailing the completed form to BPV within 24 hours of the site becoming aware of the event. Once the EDC is available, the information should be entered in the AE eCRF.

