For each dose, if the activity level reaches 5 IU/dL and if no safety issue is found, then up to four patients will receive this dose. If at any time activity levels reach 10 IU/dL or higher, no further dose escalation will take place, but additional patients will then be dosed at this dose level for a total of 6 patients per dose.

Because patients develop neutralizing immunity upon exposure to the capsid, re-challenge of vector is not a treatment option and these patients have effectively a single opportunity for therapy using this AAV capsid. Efficacy will be determined by FVIII activity at 16 weeks post dose. Safety will be evaluated for approximately 5 years after dose. Any safety signal will trigger a review of the data and possible additional analysis including mononuclear collection. Additionally, if any of the events listed in Section 9.3.3.1 occur, enrollment into the trial will be halted to complete an extensive safety analysis. Notification of the study halt will be sent by the Sponsor to the participating sites via telephone and email immediately after becoming aware of a safety concern. This will ensure no additional subjects are dosed until the signal has been completely evaluated. If, following safety review by the Data Review Board (DRB) and the Sponsor, it is deemed appropriate to restart dosing, a request to restart dosing with pertinent data will be submitted to the health authority.

A summary of events and assessments are provided by visit in Table 9.1.1 for Screening, Baseline and BMN 270 Infusion, in Table 9.1.2 for Post-Infusion Follow-up, and in Table 9.1.3 for Safety Follow-up.

BIOMARIN	270-201 – Amendment 2	Page 33
----------	-----------------------	---------

Table 9.1.1: Schedule of Events – Screening and Infusion

	Prior to BM	IN 270 Infusion			
Assessment	Screening (Day -28 to Day -1)	Baseline (Day -7 to Day -1) ^h	BMN 270 Infusion Visit (Day 1)		
Informed consent	Х				
Medical History	Х				
Physical Exam ^a	Х	X	X		
Vital Signs	Х		X		
Assessment of Adverse Events and Concomitant Medications	Х	X	Х		
Documentation of bleeding episodes and FVIII usage (by either patient or clinical information)	Х	Х			
Electrocardiogram	Х				
Chest X-ray	Х				
Liver Ultrasound	Х				
hFVIII Assays ^b	Х	Х			
AAV5 Assays ^c	Х		Х		
Screen for Hepatitis B, Hepatitis C, HIV ^d	Х				
Blood chemistry, haematology, urine tests, coagulation screen, and CRP ^e	Х	Х			
Mononuclear cell collection for CTL baseline		Х			

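### Two of the adverse-event criteria that halt enrolment, a related Grade 3 event and a related Grade 2 event lasting 7 days, have no express deadline for reaching the sponsor when they are non-serious

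*Protocol*

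**What the plan says.** Under Section 9.3.3.1, if any one of six events occurs in a treated subject, "enrollment into the trial will be put on halt to complete an extensive safety analysis per Section 9.1". Two of the six are defined by grade and relatedness, with no mention of seriousness: "The occurrence of Grade 3 or higher adverse events assessed as related to study drug, including liver failure and clinical hepatitis", and "Grade 2 adverse event assessed as related to study drug that persists for at least 7 days". The other four are a 5-fold ALT rise, neutralizing antibodies to hFVIII, vector genome in semen beyond 26 weeks, and malignancy other than skin cancer.

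The expedited duty in Section 10.5.1 opens with "All SAEs and EOSI that occur during the course of the AE Reporting Period" and sets a limit of 24 hours from site awareness. Section 10.2.1 names one event of special interest: "Elevation of liver enzymes (ALT) that triggers a corticosteroid treatment". Table 10.3.3.2.1 makes only Grades 4 and 5 automatic SAEs, and Section 10.3.3.2 states that severity and seriousness are different things. For other events, Section 10.3.2 asks for an entry in the medical record and on the AE eCRF, without a time limit; Section 17 on case report forms gives none either.

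The purpose of the halt appears in Section 9.1 of Amendment 2, the latest version of that section shown. Sites are notified once the sponsor becomes aware of a concern, and "This will ensure no additional subjects are dosed until the signal has been completely evaluated".

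**The concern.** A halt across sites can begin only when the sponsor knows that a halt criterion has been met. If the index subject is at one site and the next subject at another, protection of the next subject depends on how fast the information travels. The list of events that stop the trial and the list of events that must be reported quickly were written separately and do not match. This is a first-in-man study with safety as its primary endpoint (Section 9.7), and each subject receives a single infusion that cannot be withdrawn. A halt rule that depends on an eCRF entry with no deadline may act too late for the subject it is meant to protect.

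**Working it through.** No sample size, power or error rate is involved. The check sets each halt criterion in Section 9.3.3.1 against the reporting routes that carry a stated clock: SAE (10.2, 10.5.1), event of special interest (10.2.1, 10.5.1), ALT report (9.4.8.2) and urgent safety measures (10.8).

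| Halt criterion (9.3.3.1) | Express clock when non-serious? | Other route |
|---|---|---|
| 5-fold ALT rise | Yes: 5 × baseline exceeds the 1.5 × baseline steroid trigger, so it is an event of special interest (24 hours) | Also a report to the medical monitor within 30 minutes (9.4.8.2) |
| Related AE, Grade 3 or higher | No for Grade 3; Grades 4–5 are always SAEs | 10.8, by judgement |
| Related Grade 2 AE lasting at least 7 days | No | 10.8, by judgement |
| Neutralizing antibodies to hFVIII | No | Laboratory result; may reach the sponsor without a site report |
| Vector genome in semen beyond 26 weeks | No | Laboratory result; as above |
| Malignancy other than skin cancer | No, if judged non-serious | Would usually be an SAE as an important medical event (10.2) |

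A literal count gives 1 of 6 criteria with an express 24-hour duty regardless of seriousness. That count overstates the practical gap. Setting aside the ALT rise (1), malignancy (1) and the two laboratory findings (2) leaves 6 − 1 − 1 − 2 = 2: the non-serious Grade 3 part of the second criterion, and the third criterion.

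The other safeguards need the same information. Section 9.4.5 requires sponsor approval before each enrolment but states no check for open halt events. Under Section 15 the Data Review Board assesses the data available to it and convenes when a signal arises. Section 10.3.3.3 commits the sponsor to prompt evaluation of reported SAEs, not of non-serious events. None of these acts on an event the sponsor has not heard about.

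The ALT provisions show that the protocol can align the two lists: there the halt criterion sits above an event that is reportable quickly, irrespective of seriousness.

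**The case against.** The strongest counter-text is Section 10.8. It requires investigators to report within 24 hours any event that may call for urgent safety measures, and seriousness is not a condition. Its three situations are offered as examples, so their silence on the halt events does not exclude them. An investigator could reasonably take an event that halts enrolment to fall under it. This stands as mitigation: it would be wrong to say that the protocol offers no route at all. But the duty depends on individual judgement, it does not mention Section 9.3.3.1, and nothing tells a site that a non-serious Grade 2 event becomes urgent on its seventh day.

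It can also be said that many Grade 3 events would be serious in any case, since the grade description includes an indication for hospitalization, and that liver failure and clinical hepatitis, the examples given, would usually qualify. That narrows the gap to non-serious Grade 3 events without closing it. Entry deadlines for non-serious events may also be set in CRF guidelines or safety plans outside the protocol; none is visible here.

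A reader might infer that up to three further subjects could be infused during the gap, because a cohort holds up to four and the first has already been dosed (4 − 1 = 3). The document does not support that figure. It gives no eCRF entry lag. Section 9.4.6.1 keeps at least three weeks between subjects, whereas the Amendment 3 revision table (entries for the synopsis and Section 9) removes that wait within a cohort once activity reaches 5 IU/dL. Section 9.1 of Amendment 3 is not shown.

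**Conclusion.** The point holds in a limited form. In the current text, a non-serious related Grade 3 event and a non-serious related Grade 2 event lasting 7 days must halt enrolment but have no express deadline for reaching the sponsor. Their coverage depends on a judgement-based reading of Section 10.8.

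Two stronger readings should be resisted. One is that five of the six halt criteria go unreported: malignancy would usually be an SAE, and inhibitor and semen PCR results may come through the laboratories, whose manual is not shown. The other is that the halt rule cannot work at all: Section 10.8, sponsor approval and the Data Review Board all reduce the risk, although the last two act only on what the sponsor already knows.

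The size is two reporting situations. The number of infusions at risk cannot be given. The mismatch rests on visible Amendment 3 text (Sections 9.3.3.1, 10.2.1, 10.3.3.2 and 10.5.1). Only the statement of what the halt is meant to ensure comes from Amendment 2.

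**What to change.** Add a second bullet to Section 10.2.1: *any event meeting a criterion in Section 9.3.3.1, irrespective of seriousness*. The 24-hour duty in Section 10.5.1 then applies without further drafting. For the persistent Grade 2 criterion, the clock would start when the site knows that the 7 days have been reached. Add a cross-reference to Section 9.3.3.1 in Section 10.8. With both in place, all 6 halt criteria carry an express 24-hour duty, against 1 of 6 as written.

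Separately, reconcile Section 9.4.6.1 with the design text recorded in the Amendment 3 revision table on the interval between subjects within a cohort, since the two disagree. Which interval applies is for the sponsor and investigators to settle.

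The cost is one bullet and one cross-reference in an amendment, and a few extra expedited reports in a trial of at most 12 subjects (Section 14.6). No dose, threshold or treatment rule changes. A confirmation from every site before each enrolment, or new laboratory flagging duties, are not needed to close this gap.
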